9.3 INVESTIGATOR APPROVAL

It is the responsibility of the investigator to obtain prospective approval of the study protocol, protocol amendments or changes, informed consent forms and other relevant documents (e.g., advertisements) from the IRB. All correspondence with the IRB should be retained at the site. Copies of IRB submissions and approvals should be forwarded to JJSV. Study sites will obtain IRB approvals and fulfill any other site-specific requirements. The investigator is required to

report to JJSV within five working days any withdrawal of approval by the reviewing IRB for his/her participation in the investigation.

Prior to the start of subject enrollment, the following documents must be signed and returned to JJSV:

- Confidentiality Agreement
- Clinical Study Agreement
- Investigator Agreement/Protocol Signature page
- Financial Disclosure form
- Signed and dated copy of investigator's current curriculum vitae
- Copy of the investigator's current medical license/number
- Hospital/Ambulatory Surgery Center Clinical Study Acknowledgement, if required

By signing the study documents, the investigator agrees to conduct this study according to the obligations above and all other applicable regulatory and legal requirements.

9.4 INVESTIGATOR INFORMATION

Information on the principal investigator at each investigative site, the coordinating investigator, the address details for each investigative site and the emergency contact details for the principal investigator of each site are listed in a separate document - Study Investigator Information.

10. EXPERIMENTAL PLAN

10.1 OVERVIEW

This study will be conducted in accordance with U.S. Code of Federal Regulations, the Declaration of Helsinki, GCP, ISO 14155 and all other applicable laws and regulations. The study will not begin until IRB approvals have been obtained.

This study will be a prospective, multi-center, open-label, post-marketing clinical study at up to 50 sites in the United States. Up to 1100 subjects will be enrolled after informed consent is obtained with up to 1000 treated subjects. Subject qualifications will be assessed at the preoperative visit according to the enrollment criteria. A subject can have either one eye or both eyes enrolled for inclusion in the study. Each eye will be tracked through the preoperative and postoperative schedule individually but only counted as a single subject.

At study start (prior to first subject implantation), each surgeons' preferred toric IOL (monofocal and presbyopia-correcting) and their average implantation volumes on a monthly basis will be collected using the SPQ (**Attachment A**).

All subjects will be examined through 3-months postoperatively according to the visit schedule described in Section 10.2, Visit Schedule.

A chart summary of all examination procedures required at each study visit is provided in **Appendix A**. Key preoperative data include visual acuities, manifest refraction, keratometry, biometry, and other routine cataract evaluation examinations and response from the SPQ

(Attachment A) will be collected prior to the first subject's operative visit for each surgeon. The operative visit will include general operative information and responses from the SHQ **(Attachment B)**, which will be collected for each implanted eye.

Key postoperative data collection at the 1-week visit for each eye will include UCDVA, medical findings/complications and surgeon satisfaction with rotational stability of the study lens. The 3-month visit will include UCDVA, manifest refraction, BCDVA, keratometry, and surgeon feedback from the SSQ **(Attachment C)** for each eye.

After the final study visit (last subject's 3-month visit) for each surgeon at each study site, surgeon feedback from the SEQ **(Attachment D)** will also be collected.

10.2 VISIT SCHEDULE

After each surgery, each eye will be examined at 1 week and at 3 months. The study visit schedule for all study eyes is outlined below in Table 3. Additional visits may be conducted at the discretion of the investigator; however, routine follow-up visits without reports of ocular adverse event(s) are not considered study visits. Unscheduled visits may be conducted as necessary at the discretion of the investigator for medically indicated follow-up.

TABLE 3: Visit Schedule for Each Study Eye

VISIT	EXAM	VISIT WINDOW
1	Preoperative Exam	Prior to 1 st eye surgery
2	Operative	After preoperative exam
3	1 week	5-14 days postoperative
4	3 months	60-120 days postoperative ^a

^a Subjects with a bilateral treatment, if both the 1st and 2nd eyes are within visit window, this visit may be done on the same day.

10.3 PREOPERATIVE PROCEDURES

All subjects enrolled in the study must sign the current IRB-approved ICD and HIPAA authorization and meet the inclusion/exclusion criteria. The informed consent must be signed before any study-specific examinations are performed, and this must be documented in the source documents.

All preoperative testing for the study must be completed prior to the first surgery. Data from routine (non-study-specific) preoperative cataract examinations performed prior to the informed consent process may be included, provided these tests are documented in the preoperative Case Report Form. If a test/exam is required by the protocol but is not part of the routine testing the investigator performs for the cataract evaluation, that test/exam is considered study-specific and is not to be done until after the informed consent has been signed by the subject. Following the informed consent process, completion of the preoperative study exam, and determination

that the subject meets all the required entrance criteria (including lens power determination), the subject may be enrolled and scheduled for surgery.

As the Informed Consent Form is signed at the beginning of the preoperative study exam, some subjects may not qualify after study-specific testing is performed. Subjects will be considered screen-failures if they do not qualify or if they qualify but decide not to proceed with surgery or study participation. These subjects will be exited from the study. If the subject has consented for both eyes to be included, and one eye screen-fails, the subject continues in the study for the other eye. If a subject is being considered for bilateral treatment, only one informed consent should be signed.

Preoperative testing to be performed for each eye includes the following:

UNCORRECTED DISTANCE VISUAL ACUITY

Monocular UCDVA is to be measured using a standard Snellen convention.

BEST CORRECTED DISTANCE VISUAL ACUITY AND MANIFEST REFRACTION

Preoperative manifest refraction is required. Monocular BCDVA is to be measured using a standard Snellen convention.

KERATOMETRY

Preoperative corneal astigmatism is to be measured by keratometry or topography.

IOL POWER AND TARGETED REFRACTION

Keratometry, axial length and anterior chamber depth (ACD) must be measured to determine the appropriate lens power for implantation. Optical biometry methods (i.e., IOLMaster®, LENSTAR®) are preferred; however, surgeons should use the biometry method that they have the most experience with. The lens power should be calculated to achieve emmetropia at distance. The IOL power A-constant used for the TECNIS Toric II is 119.3. The physician should determine preoperatively the spherical equivalent and cylindrical power of the lens to be implanted.

NOTE: Surgeon may choose to use 119.3 or personalized A-constant

SURGICAL PREFERENCE QUESTIONNAIRE (SPQ)

Each surgeon will complete a 4-item questionnaire at study start (prior to first subject implantation). The questionnaire will collect information regarding the surgeons' preferred toric IOL (monofocal and presbyopia-correcting) and their average implantation volumes on a monthly basis.

Additional preoperative information may be collected (for each eye included in the study):

- Informed consent documentation
- Subject demographic information
- Planned surgery date(s)
- Ocular history, including presence of ocular pathology

- Any significant medical findings from a slit-lamp exam, dilated fundus exam, intraocular pressure or other.

10.4 STUDY LENS SUPPLY

The Principal Investigator will implant lenses from their TECNIS Toric II inventory.

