4. STUDY DESIGN

This is a multicenter, prospective, single-arm, open-label, clinical study of the commercially available TECNIS Toric II, Model ZCU IOL. The study will be conducted in up to 1100 subjects enrolled with 1,000 subjects needing unilateral or bilateral cataract surgery across up to 50 US study sites.

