9. INVESTIGATOR SELECTION

9.1 INVESTIGATOR QUALIFICATIONS

JJSV will select ophthalmic surgeons who have completed a residency in ophthalmology (or its documented equivalent) and are licensed to practice medicine and perform surgery at his/her investigative site. Each site will have one designated principal investigator; some sites may have additional sub-investigators performing surgery for study cases.

Investigators will be selected from surgeons who are experienced in small-incision, cataract extraction and toric IOL implantation in cataract patients. Surgeons are defined as professionals with experience in handling the surgical products and are familiar with the English language. All communication between the site and the sponsor will be in English. Additionally, surgeons should have established their personalized A-constant for the TECNIS® 1-Piece lens platform.

All sites will be required to have adequate staff support for reporting and patient follow-up, as well as the instrumentation necessary to conduct study testing.

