9.2 INVESTIGATOR OBLIGATIONS

Investigators are required to fulfill the following obligations:

- Conduct the study in accordance with the relevant and current protocol and all legal requirements for clinical trials including ISO 14155 and GCP. Investigator will only make changes to a protocol after notifying and obtaining approval from JJSV and the Institutional Review Board (IRB) except when necessary to protect the safety, rights or welfare of subjects.
- Personally, conduct and supervise the study.
- Maintain a list of appropriately-qualified persons to whom the investigator has delegated significant trial-related duties.
- Be responsible for protecting the rights, safety and welfare of subjects under the investigator's care and be responsible for the control and documentation of the devices under investigation.
- Maintain confidentiality as required by HIPAA or similar laws and regulations.

- Shall not obtain written informed consent from any subject to participate or allow any subject to participate before obtaining IRB approval and regulatory approval.
- Document in each subject's case history that informed consent was obtained prior to participation in the study.
- Report to JJSV any adverse experiences that occur during the study in accordance with applicable laws and regulations.
- Read and understand the information in the DFU for the study.
- Maintain adequate and accurate records in accordance with applicable laws and regulations and make available all study documents and subject medical records for inspection by either JJSV, the U.S. Food and Drug Administration, and/or the IRB.
- Ensure the IRB that is responsible for initial and continuing review of the study complies with applicable laws and regulations.
- Report all changes in research activity and all unanticipated problems involving risks to patients to the IRB and JJSV.
- Submit progress reports on the investigation to JJSV and the reviewing IRB at regular intervals, but no less often than yearly.
- Upon completion of enrollment or termination of the study or the investigator's part of the study, or at JJSV's request, return to JJSV any remaining supply of the study product.
- Provide sufficient accurate financial information to JJSV to allow JJSV to submit complete and accurate certification or disclosure statements. Promptly update this information if any relevant changes occur during the investigation or for up to one year following completion of the study.

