ATTACHMENT A- SURGEON PREFERENCE QUESTIONNAIRE (SPQ)**Instructions**

- This questionnaire is self-administered and should be completed by the surgeon prior to the first subject being implanted in the study.
- The purpose of this questionnaire is to collect your preferred toric IOL and its implantation volume.

1) Please specify your choice for preferred monofocal toric IOL (choose one).

TECNIS® Monofocal Toric
AcrySof® IQ Toric
enVista Toric
Other, Specify _____

2) Please specify your choice for preferred presbyopia-correcting toric IOL (choose one).

TECNIS Symfony® Toric
AcrySof® IQ ReSTOR®
AcrySof® IQ PanOptix®
Trulign Toric
Other, Specify _____

3) On average how many patients do you typically implant with your preferred monofocal toric IOL on a monthly basis?

Less than 5
5 to 10
11 to 15
More than 15
Other, Specify _____

4) On average how many patients do you typically implant with your preferred presbyopia-correcting toric IOL on a monthly basis?

Less than 5
5 to 10
11 to 15
More than 15
Other, Specify _____

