ATTACHMENT D- SURGEON OVERALL EXPERIENCE QUESTIONNARE (SEQ)**Instructions**

- This questionnaire is self-administered and should be completed after the last subject's 3-month visit for each surgeon at your site.
- Please answer the questions based on your overall experience with your preferred toric IOL prior to the study vs. TECNIS® Toric II IOL (study lens).

1. How is the rotational stability of the study lens in comparison to your preferred monofocal toric IOL used prior to the study?

5- Much better	
4- Somewhat better	
3- Same	
2- Somewhat worse	
1- Much worse	

If you answered "1- Much worse" or "2- Somewhat worse", please specify reason.

2. How is the rotational stability of the study lens in comparison to your preferred presbyopia-correcting toric IOL used prior to the study?

5- Much better	
4- Somewhat better	
3- Same	
2- Somewhat worse	
1- Much worse	

If you answered "1- Much worse" or "2- Somewhat worse", please specify reason.

3. Rate your level of confidence in treating astigmatism with the study lens in comparison to your preferred monofocal toric IOL used prior to the study?

5- Much more confident	
4- Somewhat more confident	
3- Same	
2- Somewhat less confident	
1- Much less confident	

If you answered "1-Much less confident" or "2- Somewhat less confident", please specify reason

4. Rate your level of confidence in treating astigmatism with the study lens in comparison to your preferred presbyopia-correcting toric IOL used prior to the study?

5- Much more confident
4- Somewhat more confident
3- Same
2- Somewhat less confident
1- Much less confident

If you answered “1-Much less confident” or “2- Somewhat less confident”, please specify reason

5. Would you recommend the study lens to your fellow surgeons?

3- Yes
2- Maybe
1- No

If you answered “1- No” or “2- Maybe”, please specify reason.

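### A surgeon who already prefers the study lens would compare it with itself in SEQ items 1 and 3, and SPQ item 1 does not reliably identify such a surgeon

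*Combined protocol and SAP*

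**What the plan says.** Section 4 calls the product the "commercially available TECNIS Toric II, Model ZCU IOL". On supply, Section 10.4 says "The Principal Investigator will implant lenses from their TECNIS Toric II inventory". It does not say when that stock was acquired. Section 9.2 also obliges investigators, at the end of enrollment or of the study, to "return to JJSV any remaining supply of the study product". That sits awkwardly with the use of their own stock.

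On who may take part, Section 9.1 says "Investigators will be selected from surgeons who are experienced in small-incision, cataract extraction and toric IOL implantation in cataract patients". Earlier use of the study lens is neither required, excluded nor capped.

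On baseline information, Section 10.3 describes the four-item SPQ: "The questionnaire will collect information regarding the surgeons' preferred toric IOL (monofocal and presbyopia-correcting) and their average implantation volumes on a monthly basis". In Attachment A, item 1 takes a single choice. The options are "TECNIS® Monofocal Toric", two named lenses from other product lines, and *Other, Specify*. Item 3 asks the monthly volume of whichever monofocal toric lens was chosen.

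At the end of the study, SEQ item 1 (Attachment D) asks: "How is the rotational stability of the study lens in comparison to your preferred monofocal toric IOL used prior to the study". Item 3 uses the same comparator for confidence in treating astigmatism. Items 2 and 4 use the preferred presbyopia-correcting toric lens, and item 5 asks whether the surgeon would recommend the study lens.

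Section 20.3 reports the frequency and proportion of surgeons giving each SEQ and SPQ response. Section 20.1 takes all responding surgeons as the population. No table of SEQ by SPQ answer and no exclusion rule is planned.

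**The concern.** SEQ items 1 and 3 presuppose two different lenses: the one the surgeon preferred before the study, and the study lens. With a marketed product taken from the surgeon's own inventory, the plan does not guarantee that they differ. For a surgeon whose preferred monofocal toric lens was already the ZCU, the only coherent answer is *Same*, and it carries no information about how the lens compares with an alternative.

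The two items are the study's only direct comparison with other monofocal toric lenses. Section 17 says the study lens was designed for better rotational stability than the ZCT series, so surgeons coming from ZCT are the most informative respondents to item 1. They are also the surgeons who could share a tick-box with anyone already preferring the ZCU. At stake is whether the reported distribution of these two items can be read as a comparison between lenses.

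**Working it through.** **The plan's own figure.** Section 20.4 gives a precision for the primary endpoint only: 1.96 × √(0.95 × 0.05 / 1000) = 0.0135. That is 1.35 points and agrees with the stated 1.4%. The present point does not touch it. The plan gives no target or precision for the SEQ.

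**Who ends up where.** Reading SPQ item 1 against SEQ items 1 and 3:

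| Preferred monofocal toric before the study | Likely SPQ item 1 answer | SEQ items 1 and 3 | Identifiable? |
|---|---|---|---|
| ZCT | TECNIS option | Valid comparison | Only if no ZCU user ticks the same option |
| ZCU | *Other, Specify* | Lens against itself | Yes, with volume from item 3 |
| ZCU | TECNIS option | Lens against itself | No |
| Another lens | Its own option, or *Other, Specify* | Valid comparison | Yes |

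The second and third rows are the problem. The second can be found in the data, but the plan has no rule for handling it. The third cannot be found.

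**Which items are affected.** Table 2 describes the study lens as monofocal. It therefore cannot be the presbyopia-correcting comparator of items 2 and 4 if the form is answered as written. Item 5 has no comparator. Only items 1 and 3 remain.

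**Size of the dilution.** Let *b* be the share answering *better* (somewhat or much) among surgeons with a genuine comparator, and *f* the share of respondents comparing the lens with itself, all answering *Same*. Then

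- reported *better* = *b* × (1 − *f*)
- reported *Same* = *s* × (1 − *f*) + *f*, where *s* is the *Same* share among the others.

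Neither *b*, *s* nor *f* is in the documents. The values below are assumptions, with no *worse* answers, so *s* = 1 − *b*:

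| *f* | *b* = 70%: reported better / Same | *b* = 50%: reported better / Same |
|---|---|---|
| 0 | 70% / 30% | 50% / 50% |
| 10% | 63% / 37% | 45% / 55% |
| 25% | 52.5% / 47.5% | 37.5% / 62.5% |
| 50% | 35% / 65% | 25% / 75% |

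In counts, if 50 surgeons responded, 10 of them compared the lens with itself, and 60% of the other 40 answered *better*, the reported share would be 0.60 × 40 / 50 = 48%. Taking those 10 out of the denominator returns 24 / 40 = 60%. The 50 is also an assumption: the synopsis gives up to 50 sites, and Section 9.1 allows several operating surgeons at a site.

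**The case against.** The strongest reply is that the ambiguity is narrow. Sections 2, 7.1 and 17 consistently separate TECNIS Toric (ZCT) from TECNIS Toric II (ZCU), so a surgeon who knows the range would probably read the TECNIS option as ZCT and write the ZCU under *Other, Specify*. The footnote to Table 2 points to personalized A-constants for the ZCT lenses, and Section 2 calls the study lens a new platform; both suggest that the expected prior experience was with ZCT. The SEQ instructions set the preferred lens against the study lens as if they were two products. Every response category is reported, so *Same* answers remain visible. All of this stands, and it makes the problem smaller. It does not remove it: no text excludes the ZCU from the TECNIS option or from being the preferred lens, and a visible *Same* does not show whether it came from a real comparison.

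A reader might infer more than the documents support:

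- *That prior use of the study lens is never recorded.* A ZCU preference can be written in, with its monthly volume. What is lost is a ZCU preference hidden in the TECNIS option, and ZCU use by surgeons who prefer another lens.
- *That investigators were established users.* Own inventory does not show use before the study, and the return clause in Section 9.2 points the other way.
- *That the primary result is biased upward because adopters rate more favourably.* The primary item (SSQ item 1) is an absolute rating of each eye with no comparator. Nothing in the documents says that adopters rate higher. If one assumes 97% satisfaction among adopters and 93% among first-time users, the pooled figure can lie anywhere from 93% to 97%, but that spread is the assumption itself; with equal rates it is zero.

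**Conclusion.** The point holds for SEQ items 1 and 3 only. The plan allows the pre-study comparator to be the study lens, does not reliably identify the surgeons concerned, and has no rule for their answers. The effect is dilution towards *Same*. Where the genuine comparisons favour the study lens, it therefore works against that lens.

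The size is *b* × *f*: 7 points for an assumed 70% *better* and 10% self-comparison, and nothing if no surgeon already preferred the ZCU, which is possible. This rests on self-comparing surgeons answering *Same*, and on shares the documents do not give.

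The SEQ is an *other* endpoint reported descriptively, so no error rate, power or decision rule is involved. No bias in the primary endpoint is shown. Severity: minor.

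**What to change.** - In SPQ item 1, replace the single TECNIS option with two: *TECNIS Toric (ZCT)* and *TECNIS Toric II (ZCU, study lens)*.
- In Section 20.3, report SEQ items 1 and 3 with surgeons who name the ZCU excluded from the denominator, and state their number separately.
- Optionally, add one SPQ item on the number of ZCU lenses implanted before the study, for description only.
- Reconcile the supply wording of Section 10.4 with the return clause in Section 9.2.

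The cost is a small questionnaire amendment, which under Section 12 needs IRB and any applicable regulatory approval, and slightly smaller denominators for two *other* endpoint items. Version 3.0 already amended both the SPQ and the SEQ, so a change of this kind is feasible. It adds no patient burden.

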10.5 SELECTION OF THE IOL

In order to facilitate IOL selection and axis placement, JJSV provides a web-based proprietary tool, the TECNIS Toric Calculator (www.TecnisToricCalc.com) for the surgeon. Preoperative keratometry and biometry data, incision location, spherical equivalent IOL power, and the surgeon's estimated surgically induced corneal astigmatism are used as inputs for the TECNIS Toric Calculator. These inputs are used to determine the axis of placement in the eye and the predicted residual refractive astigmatism for TECNIS Toric II 1-Piece IOL models.

NOTE: *The TECNIS Toric Calculator also provides an option for including the Posterior Corneal Astigmatism (PCA) (where available). The predetermined value for posterior corneal astigmatism can be included in the calculation by checking the box labeled "Include Posterior Corneal Astigmatism (PCA)".*

